### All optional study meetings, meeting content, and duration are summarized here (for participants in NRT condition only):

Timeline	Optional Meetings / Psilocybin Session	
Week 1B (after 6-	Psilocybin prep. Meeting 1 (90 min)	
month follow-up)	Discuss previous quit attempt	
	Discuss psilocybin effects	
Week 2B	Psilocybin prep. Meeting 2 (90 min)	
	What to expect in psilocybin session	
Week 3B	Psilocybin session (8 hrs)	
	Integration meeting 1 (45 min; Next day)	
	Participant Narrative of Session	
Week 4B	Integration meeting 2 (45 min)	
	Supporting smoking abstinence	
Week 5B	Integration meeting 3 (45 min)	
	Supporting smoking abstinence	
6 months post-	Follow-up meeting (2-4 hrs)	
psilocybin		

**MRI Brain Scanning Sessions:** For the revised study protocol, up to 60 participants in the psilocybin and NRT conditions (n=30 per group) will undergo between two and four MRI brain scanning sessions (4-6 hours each), taking place at the NIDA intramural research program (IRP) on the Bayview campus under the supervision of [name]. [name] is Chief of the Neuroimaging Research Branch at the National Institute on Drug Abuse-Intramural Research Program (NIDA-IRP) and will serve as the Principal Investigator of the NIDA-IRP protocol addendum that covers all neuroimaging procedures performed in this study. Only participants demonstrating biologically verified seven-day point-prevalence smoking abstinence at the initial 3-month follow-up will be asked to undergo a final MRI scan at that time. All MRI participating volunteers will be financially compensated for their time on MRI scanning days with funding provided by NIDA IRP. Before MRI scanning, participants will provide a urine sample for a drug urine screen. MRI scanning will not proceed unless the drug screen results are negative, or unless participants pass a neuromotor evaluation showing they are not currently intoxicated, and are cleared to proceed by the NIDA study physician. NIDA IRP has resumed inperson research, and instituted COVID-19 safety measures consistent with those described in the current protocol (i.e., physical distancing, PPE and mask use during all visits, pre-visit symptom checks, thorough equipment cleaning between participants), which will be used for participant and personnel safety at in-person MRI visits. Additionally, NIDA IRP will be providing pointof-care COVID-19 testing for participants at in-person study visits. Only individuals with negative COVID-19 tests will be allowed to proceed with their scheduled visit. Otherwise they will be advised to quarantine according to CDC guidelines and required to provide negative COVID-19 test results before resuming in-person study visits as described below.

The first (optional) MRI scan may occur as part of a voluntary NIDA approved sub-study protocol, which is a large-scale (N=2500) investigation of genetic polymorphisms associated with substance dependence. If participants agree to participate in this sub-study, the related MRI scan will be completed after study-screening, and will produce an MRI scan of clinical quality to be examined for incidental findings by a Johns Hopkins Hospital (JHH) neuroradiologist. Participants who decline to complete the NIDA sub-study will receive a clinical MRI scan at their first MRI scanning visit to be examined for incidental findings by a JHH neuroradiologist. The next (required) MRI scan will take place in approximately week 2 of treatment after an initial orientation meeting, and before randomization in week 3. The following (required) MRI scan will scan will occur in approximately week 5 of treatment. For the psilocybin condition this scan will

occur one day after psilocybin administration. For the NRT condition this scan will occur immediately before initiating NRT administration. A final, conditional MRI scan will take place at 3-month follow-up only for participants demonstrating biologically verified seven-day point-prevalence smoking abstinence at that time. After completing the 6-month follow-up all participants initially randomized to the NRT condition will be eligible to undergo additional (optional) meetings including a high-dose psilocybin session. However, no further MRI scanning will be conducted after the 3-month time point.

Participants will be asked to abstain from smoking for 24 hours before all MRI scanning sessions, as verified by measures of exhaled breath CO. MRI scans will last roughly 4 to 6 hours, and be conducted at the NIDA IRP building adjacent to the BPRU by a trained MRI operator. A trained study staff member will be present during all MRI scanning sessions. Any incidental findings will be communicated by the JHH neuroradiologist to the NIDA IRP Medical Advisory Investigator, who will transmit incidental findings to [name], the Hopkins study team physician. [name] will report any incidental findings to participants at an in-person meeting, over the phone, or via mail as deemed appropriate commensurate with the significance of the findings.

**Monitor Telephone Contact:** In order to provide encouragement for smoking abstinence, and to monitor participant status after psilocybin or NRT administration, participants will receive a brief (<5 min.) telephone call or inquiry via text message from study staff every day (with the exception of days on which a monitor meeting is scheduled) for the first seven days after the TQD. An occasional day may be missed for unavoidable reasons, but efforts will be made to minimize this. Telephone discussions may continue up to 4 weeks after TQD on a less frequent basis (e.g., 3 times per week) if the study team judges that continuing daily support would be helpful. For all participants, the primary study staff member will be available 24 hours for telephone consultation, and in the case of side effects or medical issues, [name] will be available by phone.

**Cognitive-Behavioral Therapy for Smoking Cessation:** Starting with the first treatment meeting participants will be provided guidance and instructions on a variety of self-help cognitive-behavioral therapy (CBT) techniques shown to be effective in smoking cessation in controlled studies (Perkins et al., 2008; Sykes & Marks, 2001; Marks, 2005). These are easily understood techniques designed to raise the awareness of the individual about the motivations, antecedents, and consequences of smoking. Examples of these techniques include placing a rubber band around one's pack of cigarettes to serve as a cue to reduce the automatic and habitual nature of smoking, the use of a score card to record when each cigarette is smoked, and the use of easily remembered acronyms to help highlight the unpleasant aspects of smoking each time a cigarette is smoked (e.g., that the cigarette is making the person feel rotten). This program fits nicely with the proposed design, in that it includes procedures to implement both before a target-quit date, and other procedures to implement after a target-quit date. Study staff will continue to discuss these techniques with the participant during staff-participant meetings throughout the study. For a summary of CBT modules, see the study timeline table in the study design section above.

Conduct of Psilocybin Session: Participants in the psilocybin condition, as well as those in the NRT condition who elect to undergo an optional psilocybin session after the 6-month follow-up, will be instructed to consume a low-fat breakfast before reporting to the laboratory for the psilocybin session. Participants must refrain from smoking during the time of drug action on the

psilocybin session day. On the day of the psilocybin session, the last cigarette may be smoked 1 hour before psilocybin administration. Participants will be instructed to abstain from smoking and drinking alcohol for at least the next 24 hours until the post-psilocybin MRI scan has been conducted (when applicable).

Before drug administration, participants will provide a urine sample for a drug urine screen and, for females, for pregnancy testing. Sessions will not proceed unless drug tests are negative for illicit drug use, and pregnancy tests are negative. Psilocybin capsules will be administered with approximately 100 mL water. The study staff, under the supervision of the investigators, will be present in the room and available to respond to participants' physical and emotional needs during the full course of the session (at least 7 hours).

These sessions often require session facilitator(s) and the participant to be in a session room together for an extended period of time and may require periods of physical contact (e.g. for adjusting blood pressure cuff, therapeutic touch etc.). On session days, it is possible that participants may inadvertently remove PPE while under the influence of psilocybin. We will adhere to the following additional safety measures for these sessions:

- COVID-19 testing will be available for participants and facilitators prior to these meetings if there is special concern raised about the possibility of exposure during the final preparation or drug administration day. The availability of testing will be discussed during preparation.
- COVID-19 testing will be performed within 72 hours of each psilocybin session with a negative result, or written proof of such testing with negative result within 72 hours of each psilocybin session must be presented if the participant claims to have been tested. This will be required to move forward with a psilocybin administration session. Participants can alternatively bring proof of full COVID-19 vaccination being completed at least 2 weeks prior to their psilocybin session in lieu of COVID-19 testing. Vaccination status will be verified via official written documentation (e.g., CDC card or healthcare provider records) and copies will be kept on file. Study team members overseeing psilocybin sessions have presently been fully vaccinated.
- Participants will be asked to maintain social distancing procedures and use PPE in public places between the baseline visit and the day after the drug administration session.
- Session facilitators will wear a surgical mask at all times during these two visits. Facilitators will wear a face shield when there is less than 6 feet of space between any two individuals. Face shields may be omitted in cases where participants and staff have been vaccinated for COVID-19.
- Session facilitators will wear gloves when touching the participant (adjusting blood pressure cuff, helping the participant to the bathroom, etc.). Gloves may be omitted in cases where participants and staff have been vaccinated for COVID-19.
- The study team will monitor the data and guidelines on duration of vaccine effectiveness and correlate this to when the vaccine was administered to any given subject when potentially modifying COVID-19 related study safety procedures.
- A washable couch cover will be used and cleaned between participants.

- Headphones will be sanitized between participants, or disposable headphone covers will be used.

During the session, participants will lie on a couch, wear eyeshades, and listen to a program of music through headphones. The participant will be encouraged to focus her or his attention inward. The eyeshades and music are intended to encourage this inward reflection. Heart rate and blood pressure will be measured pre drug administration, at 30, 60, 90, 120 minutes after drug administration, and then hourly until at least 6 hours after drug administration and until drug effects have subsided. Sessions are expected to last 7 to 10 hours. Baseline heart rate and blood pressure will be obtained after the participant has been recumbent for 5 minutes. Around the time of each physiological measurement, monitors will use questionnaires to rate the presence and intensity of behaviors, signs, and reported symptoms, including sleepiness, amount of speech, anxiety, stimulation/arousal, tearing/crying, nausea/vomiting, yawning, restlessness, feelings of unreality, visual changes, euphoria, and peacefulness. Video and audio recordings will be made throughout the session. At the end of the experimental session, participants will complete pencil-and-paper or computer-based instruments designed to assess acute subjective experiences associated with the psilocybin session (see section 7), and will be asked to write a narrative description of the experience of the psilocybin session that evening. On the first meeting with the monitor after the session (1 or 2 days after each session), the study staff will complete questionnaires retrospectively rating various behaviors and experiences observed on the session day and reported by the volunteer during the meeting (e.g. Next-Day Monitor rating).

NRT Condition: Participants in the NRT condition will receive preparation and instructions from study staff on how to use the nicotine transdermal patch, which may be mailed to them to reduce in-person contact. Participants will receive detailed information on NRT and potential side effects prior to patch administration. On the day after their Target-Quit Date in week 5, they will be provided with a 2-week supply of medication, and instructed to begin a standard 8 to 10 week transdermal nicotine patch regimen according to recommended label usage (For individuals who smoke more than 10 cigarettes per day: 21mg daily for weeks 1-6, 14mg daily for weeks 7-8, 7mg daily for weeks 9-10. For individuals who smoke 10 or less cigarettes per day: 14mg daily for weeks 1-6, 7mg daily for weeks 7-8; FDA label, PDR.net). For MRI participating volunteers receiving NRT (n=25), the Target-Quit Date will occur 24 hours prior to the MRI scanning day in week 5, and participants will begin using NRT immediately after that MRI scan is completed. To ensure matching treatment procedures, participants randomized to the NRT condition who are not MRI participating volunteers, and are completing only the treatment portion of the protocol (n=15), will also stop smoking 24 hours prior to their meeting in week 5 (to be confirmed by breath CO). At this meeting they will receive their first 2-week supply of transdermal nicotine patches and initiate NRT use. Participants will receive additional supplies of appropriate dose patches at 2-week intervals around their regularly scheduled treatment meetings. Participants will be asked to notify study staff immediately in case of adverse events or side effects, and will determine with the study physician whether NRT dosage should be adjusted, or permanently discontinued. In the unlikely event of a severe side effect such as a myocardial infarction/arrhythmia, participants will be advised to immediately discontinue NRT use. Under these circumstances, participants will be asked to continue the study protocol meetings to completion.

After completing the 6-month follow-up, participants initially randomized to the NRT condition will be eligible to undergo an optional high-dose (30mg/70kg) psilocybin session. If they choose to take part, they will receive two weekly preparation meetings, one high-dose

psilocybin session and next-day integration meeting, and two weekly follow-up meetings. For individuals who were unsuccessful in their smoking cessation attempt using NRT, this session will serve as an additional quit attempt and provide further smoking cessation efficacy data on psilocybin pharmacotherapy in treatment-resistant populations. For participants who successfully quit smoking using NRT, this session will focus on promoting long-term abstinence. For participants from the NRT condition who choose to take part in the optional psilocybin session, their remaining follow-up meeting will be shifted to take place at 6 months after their optional psilocybin session, and follow-ups will be identical to those in the psilocybin condition, including measures of breath CO and questionnaire assessments of smoking abstinence self-efficacy, craving, withdrawal, and subjective effects of psilocybin. Participants who choose not to take part in this process will not be penalized, and will be asked to complete the study as originally planned, by attending the remaining 12-month follow-up meeting.

**Baseline and Follow-up Data Collection:** Baseline psychological data will be obtained on each volunteer at the time of enrollment. Smoking history will be collected, and several smoking related questionnaires will be administered. Psychiatric history (including family history), psychoactive drug-use history (including alcohol) and information about employment status and current functioning (including mood and psychological and psychosomatic symptoms) will be obtained using standard psychiatric instruments such as the SCID and the BSI. In addition, baseline assessments will be taken on a number of psychological variables that may be impacted by a psilocybin experience, e.g. psychiatric symptoms and mystical-type experience. Reassessment of several measures will be made throughout the study and at follow up visits. For MRI participating volunteers (N=60), functional neuroimaging (fMRI) data will also be collected in approximately weeks 2 and 5 weeks of treatment, and again at 3-month follow-up for participants demonstrating biologically verified 7 day point-prevalence smoking abstinence at that time point. A thorough description of measures and the time of their assessment is included in section 7.

Assessment of Smoking Cessation: Participants will complete smoking assessments (including biological verification and other measures as shown in section 7) at 1 to 2 week intervals throughout the course of the study. These assessments will include biological verification of smoking status with breath carbon monoxide during the 13-week treatment period. Additionally, urine cotinine samples will be collected at screening, and at 3, 6, and 12-month follow-ups. Participants will have meetings in weeks 6, 7, 9, 11, and 13 after their initial TQD to provide self-report data on smoking behavior, exhaled breath samples, and to complete questionnaires. All participants will have follow-up meetings at 3, 6, and 12 months post-TQD, or at 3 and 6 months post-TQD, and 6 months post-psilocybin administration for participants in the NRT condition who choose to undergo an optional psilocybin session. Breath samples may be taken remotely using an individually assigned mobile CO breath monitor device, and urine samples may be provided remotely by mail or tested at home.

#### b. Study duration and number of study visits required of research participants.

The pre-treatment phase of the study, including screening, enrollment, and sub-study protocol completion will require at least two full days (approx. 4-6 hours each) of meetings. Because of the large number of screening measures, screening and intake for either group may require 2 appointments. The treatment phase of the study, including treatment meetings, psilocybin session

(when applicable), and MRI scans (when applicable) will require 11 meetings over approximately 13 weeks. For the post-treatment follow-up phase of the study, participants will have meetings at approximately 3, 6, and 12 months post-target quit date for follow-up assessment (2-4 hours each). Additionally, participants from the NRT group who choose to partake in an optional psilocybin session will undergo six supplementary meetings, including two weekly preparatory meetings, one high-dose psilocybin session and next-day integration meeting, and two weekly follow-up meetings to assess psychological and smoking status. However, participation in these optional meetings will not substantially affect overall study duration. Thus, the study will comprise a total of approximately 16-22 study meetings over the course of roughly 14 months. Participants who are not participating in MRI scanning (n=40) will have the same number of study visits as those who undergo NIDA MRI scanning (n=60), though study visits in weeks 1, 2, 5, and potentially 3-month follow-up will be approximately 4-5 hours shorter in duration.

#### c. Blinding, including justification for blinding or not blinding the trial, if applicable.

Because of the distinctive nature of the two treatment protocols, and the different preparation required for each (e.g., single day-long psilocybin session vs. 8 to 10 week daily nicotine transdermal patch use), blinding will not be utilized.

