#### 3. Study Procedures

### a. Study design, including the sequence and timing of study procedures (distinguish research procedures from those that are part of routine care).

Study design: For this revised study protocol we will randomize 80 participants to complete a 13-week cognitive-behavioral therapy treatment protocol involving either a single high-dose (30mg/70kg) administration of psilocybin, or an 8 to 10 week course of NRT (transdermal nicotine patch) for smoking cessation. Participants will be nicotine-dependent cigarette smokers, who have had multiple unsuccessful quit attempts, and who continue to desire to quit smoking. Other than nicotine dependence, participants will be physically and psychologically healthy. In total, 95 participants will complete the study, including 15 individuals who have already completed psilocybin-facilitated treatment before the current protocol modifications, and 80 further individuals to be recruited for the revised study design including NRT control arm. Fifty participants will also undergo MRI data collection before and after treatment to inform neurobiological mechanisms of action. After screening and enrollment, participants will complete several baseline measures, and those who have consented to participate in the MRI scanning component will be invited to participate in an optional NIDA sub-study protocol. Participants will begin a 13-week cognitive-behavioral smoking cessation program consisting of weekly meetings with two trained study staff members for weeks 1-7 of study treatment, and meetings every other week thereafter (i.e., weeks 9, 11, and 13). For the revised study protocol up to 60 participants will undergo an MRI scan in week 2 of study treatment, and will be required to abstain from smoking for 24 hours before all MRI scans as verified by breath carbon monoxide measures. An additional 30 individuals who do not meet MRI scanning inclusion criteria (e.g., are left handed), but are otherwise eligible to enroll, will complete only the treatment-related portions of the study. During the third treatment meeting in week 3, participants will be randomized into one of two treatment conditions (i.e., psilocybin or NRT).

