Volunteers who fail screening at BPRU but who, in the judgment of the investigators, might be eligible for a future study will be asked to complete IRB-approved HIPAA-IRB Form 3 "Authorization to contact you about future research studies." Volunteers' files will be kept in a locked room and treated as confidential research material. All data will be collected using the unique identification code numbers assigned to each volunteer upon entry to the study. No individual identifiable information will be released without written authorization. These procedures have been used in the past to protect confidentiality of study data and no instance of loss of confidential information has occurred.

Two hundred volunteers will sign consent to be screened to provide 130 participants who start the study, and 115 participants to participate until completion. Consent will be obtained at BPRU at a scheduled meeting after volunteers have passed telephone screening. Due to COVID-19 space restrictions, participants and study staff may review the consent form remotely or onsite in separate rooms over a secure online platform (e.g., Zoom) to go over study procedures and answer questions before signing consent. Informed consent will be signed at BPRU in-person. Participants will be provided an information sheet about COVID-19 per JH SOM Research Visit Guidelines, as well as information about personal protective equipment (PPE) requirements for their upcoming visit. Participants will be encouraged to socially distance per national and regional guidelines. Written informed consent will be updated to reflect the measures described herein.

Participants will complete a pre-visit COVID-19 symptom questionnaire within 24 hours of all in-person visits, and/or be screened with a symptom questionnaire upon arrival at the Behavioral Pharmacology Unit (BPRU). The screening questionnaire will assess for possible COVID-19 symptoms including:

- Elevated body temperature
- Presence of cough
- Loss of smell or taste
- Presence of fatigue or general malaise
- Presence of headache
- Presence of body aches
- Adherence to social distancing guidelines
- Known contact with an individual who tested positive for COVID-19 in the past 14 days

• Engagement in high-risk behaviors (e.g. participation in large gatherings without social distancing or use of PPE)

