#### 6. Study Statistics

#### a. Primary outcome variable.

The primary outcome variable will be between group differences of biologically verified (i.e., CO, cotinine) and self-reported smoking abstinence 6 months post-TQD, with a grace period for initiation of abstinence within 14 days of the TQD. This outcome meets success criteria used for FDA evaluation of smoking cessation medications.

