#### Longitudinal measures (Smoking related):

#### Carbon monoxide breath and cotinine urine samples as biological measures of smoking:

These two measures are widely used in smoking cessation studies and provide advantages that complement each other. The carbon monoxide measure, assessed using expired air samples (e.g., Bedfont Smokerlyzer, Bedfont iCO mobile smokerlyzer) can detect very recent smoking and provides immediate results to study staff, but cannot detect smoking that occurred over 24 hours ago. The cotinine assay is collected with urine samples and will not provide results for several days because samples must be sent to an outside laboratory (e.g., Friends Research Institute). However, cotinine assays provide a larger time window of detection, with the ability to detect smoking that has occurred during approximately the last 6 days (SRNT Subcommittee on Biological Verification, 2002). Breath samples may be taken remotely using an individually assigned mobile CO breath monitor, and urine samples may be provided remotely by mail or tested at home.

*Fagerström Test for Nicotine Dependence* (FTND): This 6-item questionnaire is widely used to characterize the level of dependence of cigarette smokers (Heatherton, Kozlowski, Frecker, & Fagerström, 1991).

*Smoking History Questionnaire* (SHQ): This questionnaire permits collecting smoking data such as age of smoking initiation, parent and peer smoking behavior, history of quit attempts, and current level of smoking (DiClemente et al., 1991).

*Smoking Abstinence Self-Efficacy* (SASE): This questionnaire provides a measure of a smoker's confidence in his or her ability to not smoke in 20 challenging hypothetical situations (DiClemente et al., 1985).

*The Wisconsin Smoking Withdrawal Scale* (WSWS): The WSWS is a 28-item questionnaire designed to assess withdrawal DSM-IV symptoms and other signs of withdrawal (Welsch et al., 1999), and provides 7 construct subscales (anger, anxiety, sadness, concentration, craving, sleep, and hunger). The WSWS subscales have shown good reliability and have been validated in smoking abstinence and nicotine replacement therapy studies (Shiffman et al., 2004).

*Questionnaire on Smoking Urges* (QSU): This 32-item questionnaire of smoking craving provides two dimensions (anticipation of pleasure from smoking, and anticipation of relief from negative affect and withdrawal), and has shown sensitivity to smoking cessation (Tiffany & Drobes, 1991).

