#### c. Statistical plan including sample size justification and interim data analysis.

This is a pilot comparative efficacy study with a randomized control condition. Demographics and smoking history at baseline will be examined for between group differences using Fisher's exact tests and independent-samples t-tests. The primary outcome variable will be a between group comparison of the percent of volunteers who show biologically verified (via carbon monoxide and cotinine measures) and self-reported smoking abstinence post-TQD, allowing for a grace period for initiation of prolonged abstinence within 14 days after the target-quit date in line with current recommendations for best practices in smoking cessation clinical trials (Piper et al., 2020). For this primary analysis, positive cotinine samples will be counted as smoking abstinent if the person indicates on the TLFB that they have used non-smoking forms of nicotine. This comparison will be performed using a logistic regression analysis, with treatment condition

as the predictor variable and prolonged abstinence as the examined outcome. Although the study sample will be small, these results will provide useful preliminary data indicating whether follow up investigation in this area is warranted. Between groups comparisons of secondary measures will examine differences across treatment conditions on variables such as smoking urges and withdrawal using independent-samples t-tests. We will apply a 2-step approach when assessing between-group differences in these variables. First, we will compare values between all participants still enrolled in the study at 6-months post-TQD, then only among those still smoking at 6 months post-TQD according to 7-day point prevalence criteria. In order to rule out the role of alternative sources of nicotine in achieving smoking abstinence, we will perform a secondary analysis where participants who stopped smoking tobacco cigarettes and initiated alternative forms of nicotine use (e.g., e-cigarettes, smokeless tobacco) will be coded as non-abstinent.

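### Section 3c rules out all blinding for a reason that does not reach whoever derives the 6-month abstinence variable; that step should follow a written rule, be done without arm, and be locked before arm is merged

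*Combined protocol and SAP*

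**What the plan says.** Section 3c gives one reason, "Because of the distinctive nature of the two treatment protocols, and the different preparation required for each", and one conclusion for the whole trial: "blinding will not be utilized". It makes no distinction by role.

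Section 6a defines the primary outcome as the between-group difference in "biologically verified (i.e., CO, cotinine) and self-reported smoking abstinence 6 months post-TQD", with 14 days' grace after the target quit date (TQD) for abstinence to begin. Section 6c calls the outcome prolonged abstinence, tests it by logistic regression on treatment condition, and adds that "positive cotinine samples will be counted as smoking abstinent if the person indicates on the TLFB that they have used non-smoking forms of nicotine".

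Two data-handling statements bear on masking. The accrual and screening text in Section 3a says that "All data will be collected using the unique identification code numbers assigned to each volunteer upon entry to the study"; this is offered as a confidentiality measure. Section 6b says that cotinine "samples must be sent to an outside laboratory", and also allows urine to be mailed in or tested at home.

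**The concern.** The stated ground explains why participants, session staff and NRT counsellors must know the treatment. It says nothing about people who work only on records. The most important of these is whoever derives the 6-month abstinence variable, since that variable is the primary result.

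In an open-label trial run by the team developing the intervention, knowledge of arm at this step is a source of bias that can largely be avoided. Section 2 says the results will indicate whether a larger controlled study is warranted, so the direction of doubtful calls matters even in a pilot. The same reasoning applies, with less weight, to image quality control, preprocessing and first-level models, none of which needs the arm.

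**Working it through.** The documents give no figure to reproduce on this point, so the check is mainly textual.

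**1. Whom the stated reason reaches.** Different treatments and different preparation are visible to those who receive or deliver them. Someone working from ID-coded records need not see them.

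**2. Whether another section restores masking.** Sections 3a, 6a, 6b and 6c contain no statement that the endpoint deriver, laboratory, image analysts or statistician work without arm. Elsewhere, blinding is mentioned only in describing cited studies, and masks are protective equipment.

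**3. Whether the derivation leaves discretion.**
- *Cut-offs.* Section 6b describes how far back CO and cotinine can detect smoking (24 hours and about 6 days) but gives no value separating smoker from abstainer. Sections 6a and 6c give none either.
- *Lapses.* Section 6c requires prolonged abstinence starting within 14 days of TQD. It does not say what amount of smoking ends it, or whether a positive CO at an intermediate visit does.
- *Start of the window.* The Section 3a schedule table lists TQD for the NRT arm at the week 5 scan and again at treatment meeting 6 in week 6. The NRT condition text in the same section puts it 24 hours before the week 5 scan or meeting. Weeks 5 and 6 are about 7 days apart, and 7/14 = half of the grace period. The psilocybin column has a single TQD. These passages must be reconciled.
- *Cotinine override.* This is a fixed rule: a positive sample counts as abstinent if the timeline follow-back (TLFB) shows non-smoking nicotine. It leaves no comparable discretion.

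**4. Whether masking is workable.** ID codes are assigned at study entry and randomization is in week 3, so the codes need not carry arm. Patches start in week 5 and run 8 to 10 weeks, so scheduled use ends well before the 6-month visit. Applying the 14-day window, however, means reading TLFB entries from the weeks when NRT participants are starting patches, and those entries can reveal arm.

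**5. Scale, for illustration only.** The Abstract randomizes 100 (50 per arm if split equally); Section 3a randomizes 80 (40 per arm). One participant is 1/50 = 2.0 points or 1/40 = 2.5 points of an arm's rate.

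For the planned logistic regression, assume two-sided 0.05 and 20% abstinence on NRT; neither figure is in the documents. With a and b abstinent and non-abstinent on psilocybin, and c and d on NRT, z = ln(ad/bc) / √(1/a + 1/b + 1/c + 1/d).

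| Per arm | Psilocybin | NRT | Calculation | p |
|---|---|---|---|---|
| 40 | 17 | 8 | 1.084/0.508 = 2.13 | 0.033 |
| 40 | 16 | 8 | 0.981/0.510 = 1.92 | 0.055 |
| 50 | 20 | 10 | 0.981/0.456 = 2.15 | 0.032 |
| 50 | 19 | 10 | 0.897/0.458 = 1.96 | 0.0503 |

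Any test on counts has a threshold between two adjacent counts, so the table shows only how much one decision can matter near it. It does not show that such a decision is likely.

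**The case against.** The strongest reply is that Section 3c answers a form question about blinding the trial, and its silence on data handling is not a decision to code with arm known. That is fair. A reader might infer that the plan has the endpoint coded by someone who knows the arm; the documents do not say who derives it or what that person sees. What stands is that the blanket statement leaves this open and nothing else closes it.

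A second reply is that the remaining gaps are gaps of definition, which a written algorithm would close whoever runs it. This is largely right, and the algorithm is therefore the first part of the fix. Masking is still useful for cases the algorithm leaves unresolved.

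Third, masking has limits. A reader might suppose that the ID codes make it free. They do not, because the arm list must be withheld and early patch entries redacted where feasible. Self-report, staff-collected CO and home-tested urine stay open whatever is done. Interview content can be expected to disclose the psilocybin session, so masking interview coding is not worth asking for.

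A reader might also infer that the cotinine laboratory knows the arm. Nothing supports this: it is an outside laboratory and data are held under ID codes. One confirming sentence is enough.

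Finally, this is a pilot with biological verification, and imaging serves a secondary objective. Both lower the stakes without removing the reason for a cheap safeguard.

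**Conclusion.** The point holds in a limited form. Section 3c rejects all blinding on a ground that covers only participants and treating staff, and no section keeps arm from whoever derives the primary variable. That derivation has real discretion in cut-offs, lapses and the NRT quit date, although not in the cotinine override.

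The documents do not support a numerical estimate of bias. They state no abstinence rates, no planned interval and no basis for a miscoding rate, so comparing coding errors with an expected interval width would rest wholly on assumed rates. The 2 or 2.5 points per participant indicates scale only and depends on which randomized total applies. The change is worth making because it reduces an avoidable bias at low cost; it does not make the trial blinded.

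**What to change.** Rewrite Section 3c by role, with matching text in Section 6c:

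1. Participants and treating staff in both arms are open-label.
2. The 6-month abstinence variable is derived by a pre-specified algorithm covering CO and cotinine cut-offs, the lapse rule, the 14-day window and the existing cotinine/TLFB rule. The NRT target quit date in Section 3a is reconciled first.
3. The algorithm is run on ID-coded files without the arm list. Unresolved cases are decided by existing staff without arm, with patch entries redacted where feasible.
4. The variable is locked before arm is merged.
5. One sentence confirms that laboratory samples carry only the ID code.
6. Image quality control, preprocessing and first-level models are run without arm.

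The cost is some data-handling work: a separate arm list, redaction and a lock step, using existing staff and codes. Sample size, visits and treatment do not change. The revised text should admit that early patch entries can reveal arm and that self-report, staff-collected CO and home-tested urine remain open.
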